PROTOCOL & CLINICAL TRIAL OUTLINE: Neurolens and Contact Lens Discomfort

NCT05801991

Principal Investigator: [name], OD, PhD

Document Date: 3/10/2025

Study Title: Neurolens and Contact Lens Discomfort

Study Site: The Southern California College of Optometry at Marshall B. Ketchum University

Ketchum Health: [name]

PROTOCOL & CLINICAL TRIAL OUTLINE: Neurolens and Contact Lens Discomfort

NCT05801991

Principal Investigator: [name], OD, PhD

Document Date: 3/10/2025

Background & Rationale

Discomfort is the primary reason for contact lens dissatisfaction and discontinuation.¹⁻³ Symptoms of contact lens discomfort are often attributed to dryness; however, severity of dry eye and discomfort symptoms is not correlated with clinical dry eye severity.^{4,5} When clinical signs of contact lens discomfort and dryness misalign with symptom severity, the possibility of an under-recognized etiology must be considered.

Symptoms associated with contact lens discomfort are similar to symptoms reported with binocular vision disorders and accommodative and vergence strain.⁶ Eyestrain, fatigue, and increased/more frequent end-of-day symptoms are noted by patients in both groups of conditions.⁶ It has been reported that uncomfortable contact lens wearers have an unusually high prevalence of binocular vision disorders and clinical signs.⁶ Basic optical calculations show that myopes must converge and accommodate more when corrected with contact lenses versus spectacles,⁷ so it is reasonable to hypothesize that a myopic contact lens wearer may experience eyestrain and discomfort associated with vergence fatigue while wearing contact lenses, but not while wearing single vision spectacles.

neurolens® is a type of spectacle lens that uses contoured prism to alleviate vergence demands and fatigue at near and, therefore, encourages comfortable vision.⁸ This spectacle design uses the neurolens® Measurement Device (nMD) to measure eye alignment and determine the spectacle lenses that are uniquely designed for each wearer.⁸ Acknowledging that some amount of contact lens discomfort may be caused by vergence fatigue, it is possible that uncomfortable contact lens wearers who wear neurolens® over their contact lenses will achieve discomfort relief.

Objective & Hypothesis

The objective of this study is to determine how neurolens® influences contact lens discomfort in uncomfortable myopic soft contact lenses wearers. We hypothesize that uncomfortable soft contact lens wearers are experiencing some level of discomfort associated with increased vergence demand when looking at near targets and will experience discomfort relief when wearing neurolens® over their habitual soft contact lenses. Uncomfortable, myopic soft contact lens wearers will be recruited. Each participant will be masked and randomly assigned a placebo pair of spectacles or a neurolens® spectacle pair for approximately one month.

Study Design

A prospective, randomized clinical trial will be performed. Participants and investigators will be masked to the treatment.

Sample Size

This is the first study to explore the relationship between contact lens discomfort and neurolens® correction. The nature of this study is, therefore, exploratory and the data and results collected will be pilot in nature. A reasonable sample size goal has been determined to be 30-60 total participants (15-30 per treatment group).

PROTOCOL & CLINICAL TRIAL OUTLINE: Neurolens and Contact Lens Discomfort

NCT05801991

Principal Investigator: [name], OD, PhD

Document Date: 3/10/2025

Primary Outcome Variable

The primary outcome variable will be change in contact lens discomfort, as measured by the Contact Lens Dry Eye Questionnaire-8 (CLDEQ-8).^{9,10}

Secondary Outcome Variables:

Secondary outcome variables will be change in symptoms scores measured on the Convergence Insufficiency Treatment Trial (CISS), Headache Impact Test (HIT-6), and the Standard Patient Evaluation of Eye Dryness (SPEED).¹¹⁻¹³

Inclusion Criteria & Study Procedures:

Table 1 lists all study inclusion and exclusion criteria. Figure 1 outlines the general flow of the study design.

Study Materials

The neurolens® Measurement Device (nMD2; neurolens, Inc. Costa Mesa, CA) and the neurolens spectacle lenses are Class 1 Medical Devices (exempt).

The nMD2 is a desktop diagnostic instrument. The following is the description provided in the manufacturer's nMD2 Users Manual:

The nMD2 is a microprocessor-controlled system used to measure eye misalignment at distance and near. Eye misalignment is measured through a dissociative test where the eyes are shown independent non-fusible targets, and direction of gaze is measured. This measurement is combined with an associative test where peripheral fusion is attained, and central alignment is measured. Effectively this measurement of eye alignment is an objective measurement of the angle of strabismus, and/or an evaluation of binocular vision.

The nMD2 uses an eye tracking system along with a stereoscopic display to measure eye alignment at distance and at near. From this information, a nMD2 number is calculated which is to be used along with other clinical assessments in the diagnosis and management of visual disorders.

The neurolens spectacle lenses include a proprietary contour prism design that provides the patient with increasing prism from the distance to near portion of the lens. The prism value used in this study will be determined using the nMD2 device. No significant adverse events/risks are anticipated for any participant who is examined with the nMD2 device.

All other study materials and instrumentation are those that are used in a normal eye examination, including anterior segment slit lamp assessment with sodium fluorescein staining and Schirmer tear volume assessment. No significant adverse events/risks are anticipated for any participant who participates in the study and/or undergoes any study procedures.

PROTOCOL & CLINICAL TRIAL OUTLINE: Neurolens and Contact Lens Discomfort

NCT05801991

Principal Investigator: [name], OD, PhD

Document Date: 3/10/2025

Table 1: Inclusion/Exclusion criteria

- Uncomfortable soft contact lens wearers (CLDEQ-8 \geq 17 points)¹⁰
- Adult, pre-presbyopic age range (18 – 35 years)
- Visual acuity of 20/25 or better in each eye with habitual contact lenses
- Soft, spherical, single vision soft contact lens wearer:
 - *Habitual contact lens sphere power -0.75 D or more myopic
 - *Habitual contact lens are spherical design
 - *Habitual soft contact lenses are single vision design
 - *Valid contact lens prescription at the date of the baseline
- No significant subjective over-refraction in either eye with habitual soft contact lenses
 - *Sphere: \leq 0.50 D myopia, \leq 0.50 D hyperopia
 - *Cylinder: \leq 0.75 D
- No history of ocular surgery
- No history of ocular disease, amblyopia, strabismus, or vision therapy
- No history of neurolens or prism spectacle correction
- No history of significant vertical phoria or vertical phoria correction
- No current ocular medication use
- No significant signs of dry eye in any eye:
 - * \leq Grade 1 ocular surface staining¹⁴
 - *Schirmer score \geq 7 mm¹⁵
 - *Tear break-up time \geq 7 seconds¹⁵
- Appropriate fit and surface of habitual soft contact lenses:
 - *Sufficient movement, centration, and coverage
 - *No significant lens deposits
 - *No signs of corneal or conjunctival contact-lens related complications
- Valid measurement on the neurolens® Measurement Device (nMD2)
 - *A numerical neurolens value
 - *Acceptable Measurement Quality Index (MQI)
 - *No low MQI (<0.8) or convergence excess

PROTOCOL & CLINICAL TRIAL OUTLINE: Neurolens and Contact Lens Discomfort

NCT05801991

Principal Investigator: [name], OD, PhD

Document Date: 3/10/2025

Participant Screening

Potential participants in the MBKU community will be contacted via email and print advertisements. Participants will contact an investigator by phone, email, or QR code (contact information will be included in the email/flyer) to determine if they may qualify based on basic inclusion criteria including the CLDEQ-8 survey. The intended population that will be recruited are members of the MBKU community (students, faculty, staff) via MBKU email addresses (anyone with email address). Please see the Protocol for more details on recruitment. Interested participants will be instructed via printed and emailed advertisements to contact study coordinators via email, phone, and/or QR code as described below:

If potential participants contact study coordinators by email, study coordinators will call the interested participant and perform screening over the phone. The CLDEQ-8 will be administered verbally to determine initial eligibility, and then all other inclusion criteria that can be verified verbally will be confirmed over the phone. If the participant meets this inclusion criteria screening, they will be invited for a baseline examination.

If potential participants contact study coordinators over the phone, The CLDEQ-8 will be administered verbally to determine initial eligibility, and then all other inclusion criteria that can be verified verbally will be confirmed over the phone. If the participant meets this inclusion criteria screening, they will be invited for a baseline examination.

If potential participants utilize the QR code included on the advertisement, the QR code will lead them to an online version of the CLDEQ-8 that the potential participant will complete. If their score qualifies them for the study, they will be instructed to contact study coordinators via phone or email. The study coordinators will then complete screening as described above.

The score obtained on the pre-screening CLDEQ-8 will not be used in the study.

Baseline Examination, Participant Enrollment, & Randomization

The baseline and enrollment examination is expected to last approximately one hour. At the baseline examination, all inclusion criteria will be confirmed again. Informed consent and HIPAA forms will be distributed to and signed by each participant. Participants will be asked to bring a copy of their current contact lens prescription and/or the boxes/blister packages of their current contact lenses to confirm prescription information.

Visual acuity will be measured monocularly with the habitual soft contact lenses at distance (approximately 6 meters) with a high contrast Snellen chart. Subjective over-refraction will be performed using a phoropter. These measurements will not influence eligibility for study inclusion. The CLDEQ-8, CISS, HIT-6, and SPEED questionnaires will be administered on an iPad.

The fit of the habitual soft contact lenses will be assessed with a slit lamp. The lenses will be removed and the patients will wait approximately ten minutes to allow the tear film to equilibrate. The neurolens® Measurement Device will then be used to obtain objective binocular vision measurements while the contact lenses have been removed, the tear film has equilibrated, and before topical fluorescein has been instilled. Topical fluorescein will be instilled to measure ocular surface staining and tear break-up time. General corneal, conjunctival, and anterior segment health will be assessed in the slit lamp. Schirmer

PROTOCOL & CLINICAL TRIAL OUTLINE: Neurolens and Contact Lens Discomfort

NCT05801991

Principal Investigator: [name], OD, PhD

Document Date: 3/10/2025

strips will be instilled in the lower temporal canthus of the right eye for five minutes to determine Schirmer score.

Once all inclusion criteria have been confirmed, participants will be enrolled and assigned to a treatment group. Participants who do not meet all inclusion criteria will be excused from the study and compensated for their time (\$50). Participants who meet all inclusion criteria will be informed that they will receive their study compensation (\$100) upon completion of the study at the final visit.

Randomization to treatment group will be achieved using an online random number generator to determine the order of allocation (1:1) before subject enrollment. Participants will be enrolled and assigned to a treatment group in the order they qualify for enrollment at the baseline examination.

Enrolled participants will be provided with a \$100 credit card cash gift card to offset the cost of spectacle frames that can be purchased at the Ketchum Health University Eye Center Optical, or they can provide their own spectacle frame. Once a frame has been identified, it will be sent to the neurolens® lab for fabrication and placement of lenses depending on treatment group assignment. Participants in the placebo group will receive single vision plano lenses. Participants in the neurolens® group will receive lenses based on the measurements made by the neurolens® Measurement Device.

Participants will be contacted when their completed spectacles have arrived. At pick-up, each participant will be instructed to wear the spectacles full time over their habitual contact lenses. At this time, they will schedule the final study visit 35 ± 5 days after spectacle pick-up.

Final Examination

The final examination is anticipated to last approximately 30 minutes. At the final examination, participants will be instructed to return wearing their habitual soft contact lenses and the spectacles dispensed at the last visit. Visual acuity will be measured monocularly with the habitual soft contact lenses and study spectacles at distance (approximately 6 meters) with a high contrast Snellen chart. The spectacles will be removed and repeat measurements will be taken using the neurolens® Measurement Device. Participants will complete the CLDEQ-8, CISS, HIT-6 and SPEED surveys. Participants will be asked to report approximately how many hours per day and days per week they wore their contact lenses, and the same parameters for their time wearing the contact lenses with the study spectacles over the last 35 ± 5 days.

After all measurements and surveys have been completed for all subjects, participants will be unmasked to the treatment group they are in. Both groups will be able to keep the spectacle lenses dispensed in the study, will be compensated for their time at both visits (\$100), and will be dismissed from the study.

PROTOCOL & CLINICAL TRIAL OUTLINE: Neurolens and Contact Lens Discomfort

NCT05801991

Principal Investigator: [name], OD, PhD

Document Date: 3/10/2025

[figure not shown]

Figure 1: Flow chart of study procedures

Informed Consent and Patient Privacy

Upon arriving at the baseline examination visit, all participants will sign an informed consent form. The form will explain the purpose of the study, any anticipated risks/benefits, and the rights the participant has. Each participant will be able to ask investigators questions and keep a copy of the informed consent form. As well, all participants will sign a Health Insurance Portability and Accountability Act (HIPAA) explaining that their health information is private and any personal health identifiers collected in the study will not be used in association with their identity and/or for any other purpose. Additionally, all participants will read and sign the MBKU COVID research consent document.

Statistical Analyses

Statistical analyses will be performed to compare the survey scores of the two treatment groups before and after treatment. ANOVA and/or Wilcoxon Rank testing will be used depending on the distribution of the data according to Shapiro statistics. Additional analyses will also be performed to determine if particular demographic information (gender, age, etc.) and/or clinical data (refractive error, wear time, etc.) influenced symptom changes as measured by the four surveys administered.

PROTOCOL & CLINICAL TRIAL OUTLINE: Neurolens and Contact Lens Discomfort

NCT05801991

Principal Investigator: [name], OD, PhD

Document Date: 3/10/2025

References:

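### The only CLDEQ-8 baseline is also an entry score and predates an open-ended lens wait; ANCOVA plus a repeat score at pick-up would buy precision and a cleaner within-arm change

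*Combined protocol and SAP*

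**What the plan says.** The protocol's Primary Outcome Variable section defines the endpoint as change in CLDEQ-8, and Table 1 requires a CLDEQ-8 of at least 17 for entry.

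The scale is given three times:

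- **Pre-screening**, by phone or online, for initial eligibility. Participant Screening then sets this score aside: "The score obtained on the pre-screening CLDEQ-8 will not be used in the study".
- **Baseline examination.** "At the baseline examination, all inclusion criteria will be confirmed again", and "The CLDEQ-8, CISS, HIT-6, and SPEED questionnaires will be administered on an iPad". Assignment follows at the same examination.
- **Final examination.**

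Between the second and third, the spectacles are made: "Once a frame has been identified, it will be sent to the neurolens® lab for fabrication". Participants are contacted when they arrive; no duration or upper limit is given. The handover is described as follows: "At pick-up, each participant will be instructed to wear the spectacles full time over their habitual contact lenses". The final visit is booked at pick-up, for 35 ± 5 days later. The text describes instructions and scheduling at pick-up, but no questionnaire. Figure 1 is not shown in the copy reviewed, so a survey drawn there cannot be ruled out.

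Statistical Analyses names ANOVA and/or Wilcoxon testing to compare the two groups' scores before and after treatment. It names no baseline-adjusted model for the primary comparison. Sample Size sets a goal of 30 to 60 participants (15 to 30 per group) and calls the study exploratory and pilot.

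**The concern.** A score that must clear a cutoff is, on average, too high: some people pass because their measurement error was positive that day. Their next score tends to be lower with no treatment at all. Here the score that starts the change measure is such a score. It also predates treatment by an unknown wait, so any drift over that wait is counted as change on the spectacles.

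Two things are at stake. First, a within-arm fall from baseline to final mixes regression to the mean and waiting time with the effect of wearing the spectacles. That matters in a pilot whose results may inform a later trial. Second, with 15 to 30 per arm precision is scarce, and one baseline score cut off at 17 is a weaker predictor of the final score than it could be.

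**Working it through.** **The plan's own figure.** The sample size has no stated alpha, power, SD or effect size. The only check possible is 2 × 15 = 30 and 2 × 30 = 60, which agrees. For scale, at two-sided 0.05 and 80% power (assumed), the detectable difference is (1.960 + 0.842) × √(2/n): 1.02 SD at 15 per arm and 0.72 SD at 30.

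**Assumptions, none of them in the documents.** Each score is a stable true score plus independent normal error. In the source population the SD is 6, the mean 12 to 18 and the reliability ρ 0.6 to 0.8. There is no treatment effect. Entry needs 17 or more at both pre-screening and baseline.

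**Hand check with one cutoff.** The expected fall is (1 − ρ) × SD × λ(z), where z = (17 − mean)/SD and λ(z) = φ(z)/(1 − Φ(z)). For mean 12 and ρ = 0.6: z = 0.833, λ = 0.2819/0.2023 = 1.393, fall = 0.4 × 6 × 1.393 = 3.3 points.

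**Both cutoffs, by simulation (3 million people per setting).**

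| Mean, ρ | Fall, baseline to final | Fall, pick-up to final | Variance: ANCOVA on baseline ÷ change score | Variance: two covariates ÷ one |
|---|---|---|---|---|
| 12, 0.6 | 2.3 | 0.0 | 0.89 | 0.90 |
| 12, 0.8 | 1.0 | 0.0 | 0.92 | 0.85 |
| 18, 0.6 | 1.2 | 0.0 | 0.86 | 0.89 |
| 18, 0.8 | 0.5 | 0.0 | 0.91 | 0.83 |

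In the first row the discarded pre-screen brings the fall from 3.3 to 2.3 points: a partial guard. Over a wider set (mean 10 to 17, SD 5 to 7, ρ 0.6 to 0.9) the fall is 0.2 to 2.9 points with both cutoffs and 0.4 to 4.3 with the baseline cutoff alone. If the cutoff applied only at pre-screening, the fall from baseline would be about 0.

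**Between arms against within arm.** With mean 13, SD 6 and ρ = 0.75, the spurious change is −1.2 points. A test of one arm's change against zero is then falsely significant in 19% of trials at n = 15 and 35% at n = 30. The between-arm test of change rejects in 4.9%, with a mean difference of 0.00.

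**Gains net of estimating the covariates.** The variance inflation is 1 + 1/(N − 4) for one covariate and 1 + 2/(N − 5) for two.

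- *ANCOVA on the existing baseline against change scores.* The factor is 1.038 at N = 30 and 1.018 at N = 60. The smallest gain is 0.92 × 1.038 = 0.955 and the largest is 0.86 × 1.018 = 0.875, so variance falls by about 5 to 13%.
- *Adding pick-up to that ANCOVA.* The factor is 1.080/1.038 = 1.040 at N = 30 and 1.036/1.018 = 1.018 at N = 60. At N = 30: 0.90 × 1.040 = 0.936 and 0.83 × 1.040 = 0.863, a cut of about 6 to 14%. At N = 60: 0.90 × 1.018 = 0.916 and 0.83 × 1.018 = 0.845, a cut of about 8 to 15%.

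At N = 30 the second gain makes the confidence interval about 3 to 7% narrower (√0.936 = 0.967, √0.863 = 0.929).

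**The case against.** The strongest reply is that the trial already has its protection. It is randomised, masked and placebo-controlled. Both arms face the same cutoff, and the protocol describes one fabrication route for both. The placebo arm therefore estimates regression to the mean plus waiting time, and the difference between arms removes it. This stands in full. A reader might infer that the inflated baseline biases the treatment effect. The documents do not support that: it would need a wait that differs by arm, and nothing in the text suggests one.

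Second, the baseline is measured afresh after a pre-screen that is thrown away, which is a recognised safeguard. This stands in part. It shrinks the artefact, but the cutoff is applied again at baseline. The statement in the baseline section that measurements will not influence eligibility follows visual acuity and over-refraction and precedes the questionnaires, so it does not exempt the CLDEQ-8.

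Third, no within-arm test is specified. That is so; the wording allows one but does not commit to it.

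Fourth, pick-up may not be a staffed research visit, since compensation counts only two visits. Yet each participant is to be instructed and to schedule the final visit there, so an eight-item survey is feasible.

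Finally, the study is exploratory, and leaving out a second baseline is a design choice, not an error. That is fair, and it sets the weight of the point.

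**Conclusion.** The point holds as a cheap improvement in precision and interpretation. Any within-arm change from the existing baseline would carry a no-effect fall of about 0.5 to 2.3 points under the stated assumptions; a change from pick-up would carry about none. Adjusting for the score already collected is worth roughly 5 to 13% of variance, and a pick-up score as a second covariate adds a moderate further gain.

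These sizes rest on assumed SD, mean and reliability, and on true scores that do not move. The fabrication delay therefore contributes nothing to any figure above. A reader might infer that the delay is known to distort the result. The documents give neither its length nor any drift over it, so all that can be said is that it is uncontrolled and, as written, not recorded as a study variable.

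**What to change.** 1. Prespecify the primary analysis as ANCOVA of the final CLDEQ-8 on arm with the enrolment score as covariate, in place of an unadjusted ANOVA or Wilcoxon comparison of change. This needs no new data.
2. Administer the CLDEQ-8 on the iPad at pick-up. It must be completed before the spectacles are seen or worn: assignment has already been made, so the score is a safe covariate only if the spectacles cannot have influenced it. Add it as a second covariate.
3. Record the interval from baseline examination to pick-up for every participant.
4. Report any within-arm change from the pick-up score, and keep eligibility on the enrolment score.
5. State how a missing pick-up score will be handled, so that nobody drops out of the primary analysis for lack of it.

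The cost is a few minutes per participant at a contact that already takes place, one degree of freedom for the second covariate, and occasional missing pick-up scores, which would erode part of the gain.

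### The between-arm comparison of change in survey scores omits the baseline score as a covariate; ANCOVA would add a little precision at almost no cost

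*Combined protocol and SAP*

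**What the plan says.** - **Outcomes.** "The primary outcome variable will be change in contact lens discomfort, as measured by the Contact Lens Dry Eye Questionnaire-8 (CLDEQ-8"). For the secondary outcomes, "Secondary outcome variables will be change in symptoms scores measured on the Convergence Insufficiency Treatment Trial (CISS), Headache Impact Test (HIT-6") and SPEED.
- **Data collected.** The CLDEQ-8, CISS, HIT-6 and SPEED are all completed at the baseline visit (Baseline Examination, Participant Enrollment, & Randomization) and again at the last visit (Final Examination).
- **Analysis.** "Statistical analyses will be performed to compare the survey scores of the two treatment groups before and after treatment". As to method, "ANOVA and/or Wilcoxon Rank testing will be used depending on the distribution of the data according to Shapiro statistics". No covariate is named for this comparison.
- **Additional analyses.** These ask whether "demographic information (gender, age, etc.) and/or clinical data (refractive error, wear time, etc.) influenced symptom changes". Baseline survey score is not listed.
- **Allocation and size.** Allocation is 1:1 from a random number list, with no stratification described. "A reasonable sample size goal has been determined to be 30-60 total participants (15-30 per treatment group"). "The nature of this study is, therefore, exploratory and the data and results collected will be pilot in nature".
- **Entry cut.** Table 1 requires a CLDEQ-8 score of at least 17.

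**The concern.** A change score fixes the coefficient on baseline at 1. ANCOVA estimates that coefficient from the data. When baseline and final scores are imperfectly correlated and similarly spread, the best coefficient is below 1. Subtracting the whole baseline score then over-corrects, and part of any chance baseline difference between arms stays in the estimate as noise. With 15-30 people per arm such differences are not negligible. The data needed to remove the noise are already being collected.

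At stake is the width of the confidence interval for the arm difference, which is the main product of a pilot. Whether the comparison is valid is not at stake.

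**Working it through.** **1. Does any reading of the plan already adjust for baseline?** If the before-and-after comparison means a repeated-measures ANOVA, its group-by-time test with two time points equals the change-score comparison, so it does not adjust. A Wilcoxon test on change does not either. The list of covariates in the additional analyses is open-ended, but those analyses ask what influenced symptom change and are separate from the treatment comparison. No reading adjusts.

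**2. Inputs.** From the documents: 15-30 per arm, 1:1, CLDEQ-8 of 17 or more at pre-screen and confirmed at baseline. Assumed, because the documents give none: source-population CLDEQ-8 mean 12 or 15, SD 6, correlation 0.5-0.8 between any two administrations. The plan states no power or precision figure to reproduce; the sample size is a pilot goal.

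**3. Formulae.** Let k be baseline SD divided by final SD, r the correlation among those enrolled, and N the total. In units of the final variance, the variance of the arm difference is proportional to:
- change score: k² + 1 − 2rk
- ANCOVA: (1 − r²) × (1 + 1/(N − 4)), where the second factor is the small-sample cost of one covariate.

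**4. CLDEQ-8, constant treatment effect.** The entry cut lowers k and r together. Simulating the selection gives these two cases at source mean 12:

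| Source correlation | k | r | Change | 1 − r² | Ratio | N=30 (×1.038) | N=60 (×1.018) |
|---|---|---|---|---|---|---|---|
| 0.8 | 0.77 | 0.51 | 0.807 | 0.740 | 0.916 | 0.95 | 0.93 |
| 0.5 | 0.62 | 0.24 | 1.087 | 0.942 | 0.867 | 0.90 | 0.88 |

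In these two cases the variance falls by about 5% and 10% at 15 per arm, and by 7% and 12% at 30. Full simulation over both means and the whole correlation range (whole-point scores, both entry cuts applied) gives about 4-12% at 15 per arm and 6-13% at 30. At 15 per arm the mean 95% CI half-width goes from 2.67 to 2.61 points at the favourable end and from 4.05 to 3.81 at the other. For an assumed 3-point effect, power rises 2-3 percentage points at 15 per arm and 2-6 at 30. Type I error is about 0.05 for both methods.

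**5. CLDEQ-8, varying treatment effect.** With an assumed between-person effect SD of 4 points, the gain is about 2-8% at 15 per arm and 3-10% at 30.

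**6. What the removed variance is.** In the first row of the table, the slope of change on baseline is r/k − 1 = 0.51/0.77 − 1 = −0.34. Its square times k² is 0.114 × 0.593 = 0.068, and 0.740 + 0.068 = 0.808, which is the change-score variance within rounding. The whole gain is therefore the contribution of chance baseline imbalance.

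**7. CISS, HIT-6, SPEED.** With equal baseline and final variances and no narrowing by selection, the reduction is 1 − ((1 + r)/2) × (1 + 1/(N − 4)). At 15 per arm: r = 0.5 gives 1 − 0.75 × 1.038 = 22%, and r = 0.8 gives 1 − 0.90 × 1.038 = 6%. At 30 per arm the range is 8-24%.

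**8. Where the gain disappears.**
- Secondary scores: break-even is r = 2(N − 4)/(N − 3) − 1, which is 52/27 − 1 = 0.93 at N=30 and 112/57 − 1 = 0.96 at N=60.
- CLDEQ-8, source correlation 0.9, 15 per arm: a gain of 1-2% if the effect is constant, a loss of 1-2% if its SD is 4 points.
- Final scores much more spread than baseline, N=30: k = 0.75 with r = 0.7 gives a ratio of 1.03, and k = 0.5 with r = 0.5 gives 1.04. These are losses of 3-4%.

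**The case against.** The strongest reply is that this is a preference about efficiency in a study that declares itself exploratory and sets no alpha, power or decision threshold. At 15 per arm the CLDEQ-8 interval narrows by only 0.06 to 0.24 points on each side (2.67 − 2.61 and 4.05 − 3.81), and every size rests on assumed inputs. A constant treatment effect is also doubtful, because the lenses are made to each wearer's own measurement. All of this stands. It is why the point is graded low and why the varying-effect range is given beside the constant-effect one.

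A reader might go further and infer that chance baseline imbalance is a second harm on top of lost precision, or that the plan leaves it wholly uncontrolled. The documents support neither. The outcome is change, so baseline is already subtracted, though with a coefficient that need not be the best one. What remains is the same variance that ANCOVA removes, and the change-score confidence interval already allows for it.

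The larger secondary-score range is also open to challenge. Participants are selected on CLDEQ-8, and the Background describes overlapping symptoms, so selection may narrow those scores too.

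The objection does not remove the fact that the covariate is missing from the treatment comparison, or that adding it costs almost nothing.

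**Conclusion.** The point holds as a free improvement of low severity. The baseline score is collected for all four surveys and is not a covariate in the between-arm comparison of change. A reader might infer from this that the planned comparison is biased or invalid. It is not: randomisation makes the change-score difference unbiased.

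For CLDEQ-8 the expected gain is roughly 2-12% of the variance at 15 per arm and 3-13% at 30, spanning constant and varying treatment effects. This depends on the assumed source mean, SD and correlation of 0.5-0.8. Gains for CISS, HIT-6 and SPEED may be larger, but only if their baseline and final variances are equal and entry selection does not narrow them. The direction is usually favourable but is not assured at 15 per arm.

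**What to change.** Add to Statistical Analyses: the primary analysis is the between-arm difference in change in CLDEQ-8 from an ANCOVA with arm and baseline CLDEQ-8 as terms, reported with its 95% CI. Use the same model for CISS, HIT-6 and SPEED, each with its own baseline. The stated outcome is kept, because the treatment coefficient is the same whether change or final score is the dependent variable.

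Write this before unmasking, if that is still ahead. The Final Examination section places it late ("After all measurements and surveys have been completed for all subjects, participants will be unmasked to the treatment group they are in"), but the documents do not give the trial's status.

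The cost is wording and one degree of freedom per model, with the possible loss of a few percent in variance described above. No new data, visits or participants are needed.
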